2. Treatment procedures

During the LR procedure, patients were placed in the supine position, often under general anesthesia of the trachea. Operators fully exposed the surgical field and explored the location of the tumor and vascular anatomy. After blocking the first liver portal, operators ligated the liver section blood vessels and bile ducts, assessed the distance between lesions, and ensured residual liver volume. Multiple tumors were removed by en bloc resection or multiple LR with good liver function, including indocyanine green (ICG) clearance tests ^[6].

During the TACE procedure, an emulsion of mixtures of lipiodol (3–30 ml) and chemotherapeutic drugs was injected, including doxorubicin (10–50 mg), cisplatin (10–110 mg), epirubicin (10–50 mg), or oxaliplatin (100–200 mg). Afterward, either a gelatin sponge or polyvinyl alcohol foam (PVA) particles were introduced to embolize tumor-feeding vessels either selectively or super-selectively ^[7].

3. Model development

According to survival algorithms in the existing literature, 10 kinds of available AI models were developed in the training set. The details of data preprocessing and model development are shown in Supplement 1. To reduce the overfitting of survival models, the AI algorithms in the training cohort were developed by adopting K-fold cross-validation. In each fold, hyperparameter optimization was tuned by an exhaustive cross-validation grid search, and the models were refitted in the training set with the optimal score parameters. The selection criterion of the AI models was defined as a C-index ≥ 0.7 . Based on the AI models, the predictive performance (censored C-index and mean cumulative/dynamic area under the receiver operating characteristic curve [auROC]), calibration curves, and Brier score (BS) were evaluated. The BS represents the mean square difference between observed patient status and predicted survival probabilities; it ranges from 0 to 1 and is negatively correlated with the discrimination and calibration of algorithms. IBS is defined as an overall estimation of BS; a value lower than 0.25 is deemed applicable in the clinic ^[8].

4. Model estimation

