An ensemble model was developed and named the precise treatment allocation (PTA) model in our study. It could accurately predict the survival probability of each patient by alternating the different treatments. The inputs of the PTA model mainly comprise four modules: (a) liver function, such as serum albumin, serum bilirubin, and coagulative function indexes; (b) tumor burden, including serum alpha-fetoprotein (AFP), tumor size, and tumor number; (c) demographic data, such as age and gender; and (d) routine laboratory indications, such as routine blood examination and kidney function indexes. To further estimate the predictive performance of the PTA model, it was compared with other prognostic models, including widespread clinical guidelines (BCLC, BCLC B sub-classification ^[9], HKLC, and the most recent Italian Liver Cancer [ITA.LI.CA] staging system ^[10]), other tumor-burden-based models (up-to-seven model ^[11], four-and-seven model ^[12], and six-and-twelve model ^[13]), and models incorporating other parameters (hepatoma arterialembolization prognostic [HAP] score, modified HAP [mHAP] II score ^[13], mHAP III score ^[14], albumin-bilirubin [ALBI] score ^[15], and the model to estimate survival in ambulatory HCC patients [MESIAH] ^[16]), by estimating the auROC and C-index.

Here, HCC patients could achieve two potential survival rates and predicted median survival times (MSTs) by choosing TACE or LR. The ideal LR candidate is defined as a patient whose MST could be extended by more than 50% compared with the MST of primary treatment if LR is adopted in the model. Similarly, ideal TACE candidates are those with an additional survival benefit of more than 50% compared to LR allocation in TACE prediction time. Considering that BCLC and HKLC ^[17] have clearly defined LR and TACE candidates, the ideal LR and TACE candidates of the PTA model were compared with candidates recommended by these two widely used guidelines.

5. Web implementation

After train and validation, the optimized PTA model was implemented as a web

interface, which generates the MST and depict integrated survival curves composed of LR and TACE according to the clinic parameters of specific patients provided by users. Relative algorithms of web development were described in the supplement 1.

6. Statistical analyses

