LR group (4.60 [3.00;7.00] cm) than in the TACE group (6.30 [4.00;9.90] cm); (b) The tumor lesions of HCC were relatively few in the LR group (1.0 [1.0-1.0] lesion) than in the TACE group (1.0 [1.0-2.0] lesions). In addition, the liver function of HCC patients (CPS and Child-Pugh stage) varied remarkably between the LR and TACE groups. A higher proportion of Child stage B patients were included in the TACE group (17.6%) than in the LR group (11.1%). The median follow-up was 54.0 months (IQR 38.7–69.2 months) for LR therapy and 36.1 months (IQR 24.7–54.7 months) for TACE. The 1-year, 3-year, and 5-year survival probability was 91.7%, 79.6%, and 70.8% for LR allocation, respectively, while 74.8%, 41.5%, and 26.4% for TACE treatment, respectively. Although there were significant differences between the LR and TACE groups, we perceived therapy type as a pivotal factor in the AI models to simulate a real-world clinical setting, considering the precise prediction of AI technologies.

Selection of the optimal AI model

We applied 10 kinds of machine learning survival algorithms in the train cohort, of which seven AI models performed well, with the C-index > 0.7 , and were retained: (i) random survival forest (RSF), (ii) conditional survival forest, (iii) DeepSurv algorithm, (iv) Extra Survival Trees, (v) Gompertz, (vi) standard Cox proportional hazards model (CoxPH), and (vii) PTA model based on the above six models. For model estimation, the C-index and IBS of these seven AI models were displayed in the Table 2. The C-index of the PTA model was 0.854 and 0.801 in the train and validation cohorts, respectively, which were higher than other six AI models except for the RSF model in train cohort. Even though the RSF model achieved the highest C-index (0.926) in the train set, while in the validation cohort, the C-index was only 0.765, indicating the potential presence of over-fitting in the RSF model. Given the C-index of the train and validation cohorts, the PTA model derived from the above six algorithms outperformed other single-algorithm models. As expected, the IBS of the six single algorithms and PTA algorithm was far smaller than 0.25, demonstrating their capability for clinical application (Supplement 2-3).

Predictive performance of the PTA model

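### Models are retained and PTA is preferred on C-index, which scores prediction under the treatment received; no stated criterion assesses the LR-versus-TACE contrast used for allocation

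*Combined protocol and SAP*

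**What the plan says.** - **Tuning (section 3).** Models are tuned by cross-validated grid search, after which "the models were refitted in the training set with the optimal score parameters". The score is not named. Details are referred to Supplement 1, which is not part of the document.
- **Retention.** Section 3 states: "The selection criterion of the AI models was defined as a C-index ≥ 0.7". The results section on selecting the optimal model reports ten algorithms in the train cohort, "of which seven AI models performed well, with the C-index > 0.7 , and were retained". The two texts differ trivially (≥ against >).
- **Preference.** The same results section concludes: "Given the C-index of the train and validation cohorts, the PTA model derived from the above six algorithms outperformed other single-algorithm models". The figures are: "The C-index of the PTA model was 0.854 and 0.801 in the train and validation cohorts, respectively".
- **Other measures.** auROC, calibration and Brier score are also evaluated. For the integrated Brier score (IBS), "a value lower than 0.25 is deemed applicable in the clinic", and the results report that "the IBS of the six single algorithms and PTA algorithm was far smaller than 0.25". None of these is stated as a selection rule.
- **Use of the model (section 4).** Of PTA it is said: "It could accurately predict the survival probability of each patient by alternating the different treatments". Ideal candidates for LR or TACE are those whose predicted median survival (MST) under that treatment is longer by more than 50%.

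**The concern.** The C-index compares the predicted ordering of patients, each under the treatment actually given, with the observed ordering of deaths. The allocation rule needs the difference between two predictions for the same patient, one of which is never observed. A model can order patients well from tumour burden and liver function while its treatment contrast is null, or is an artefact of how patients were chosen for LR.

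The contrast produces the headline result. In the comparison with clinical guidelines, 458 LR patients and 2752 TACE patients are labelled as wrongly allocated: (458 + 2752)/4991 = 64%. The model is also offered on the web for individual use. If selection never tested the contrast, calling PTA optimal rests on evidence about prognosis.

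**Working it through.** **1. The document's own figures.** The validation C-index of 0.801 cannot be recomputed without patient data. The counts agree: 1916/4991 = 38.39%; 4192/4991 = 84.0%; 1458 + 458 = 1916; 323 + 2752 = 3075; 2752/3075 = 89.5%.

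**2. What treatment alone contributes.** From the stated survival by treatment, the crude cumulative-hazard ratio TACE/LR is ln S(TACE)/ln S(LR):
- 1 year: ln 0.748/ln 0.917 = 3.35
- 3 years: ln 0.415/ln 0.796 = 3.85
- 5 years: ln 0.264/ln 0.708 = 3.86

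Under proportional hazards without censoring, a fraction 2 × 0.384 × 0.616 = 0.473 of pairs differ in treatment. With tied predictions scored one half, the treatment label alone gives C = 0.5 × 0.527 + 0.473 × 3.35/4.35 = 0.628, or 0.639 at a ratio of 3.86. Passing 0.7 therefore needs prognostic covariates.

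**3. Can the bar be passed with no treatment effect?** Simulation with 4991 patients split 4192/799, one prognostic covariate that also drives treatment choice, LR about 38%, exponential survival, uniform censoring (12–96 months) and Cox models. Covariate strength is an assumption.

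| Covariate log-HR | Validation C | Runs passing 0.7 |
|---|---|---|
| 1.3 | 0.780 | 60/60 |
| 0.9 | not recorded | 39/40 |
| 0.7 | 0.68 | 0/40 |

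So the bar can be passed with no effect when covariates are strong. The value 1.3 was chosen to land near the reported 0.80.

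**4. Does C-index see a better contrast when confounders are measured?** Same design, log-HR of LR = −0.5 + h × modifier. Model A has main effects only; model B adds the treatment-by-modifier term. Correct allocation here means the right direction of benefit.

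| h | Validation C, A / B | Correct allocation, A / B |
|---|---|---|
| 0.6 | 0.788 / 0.794 | 79.8% / 97.3% |
| 0.8 | 0.786 / 0.797 | 73.4% / 98.2% |

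A gap of 17.5 points in correct allocation moves C by 0.006, and one of 24.8 points moves it by 0.011. All models pass 0.7. Both models are scored on the same patients, so the paired difference matters: in repeats, B had the higher validation C in 92% to 100% of runs (39/40 and 40/40 in one repeat).

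**5. Unmeasured confounding, no treatment effect.** 20 runs; measured covariate log-HR 1.2, unmeasured 1.0, both driving treatment choice; censoring 12–90 months. Simulated 1-, 3- and 5-year survival was 91.2%, 79.3% and 70.6% for LR (stated: 91.7%, 79.6%, 70.8%) and 66.5%, 42.7% and 31.4% for TACE (stated: 74.8%, 41.5%, 26.4%), so the TACE match is only rough.
- Without a treatment term: C = 0.732 (range 0.719–0.749).
- With a treatment term: C = 0.760 (0.738–0.780) and a spurious HR of 0.37. Under exponential survival the MST ratio is 1/HR, so the 50% rule is met when HR < 0.667. Here 1/0.37 = 2.7, and 100% of patients were sent to LR.
- In a further set of 25 runs, where the spurious HR was 0.62, the model carrying it had the higher C in 25/25.

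**6. Do the other measures fill the gap?** They too score prediction under the treatment received. The IBS limit is also easy to meet: a covariate-free survival curve has Brier score S(1 − S), which never exceeds 0.25. At the stated survival it is 0.076–0.207 for LR and 0.188–0.243 for TACE. The hazard ratios in the guideline comparison come after selection and within one treatment group, so a purely prognostic score could also make them large.

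**The case against.** The strongest reply is that C-index ranking is not blind to the contrast. Step 4 bears this out when the confounders are measured. A badly wrong contrast can even fail the bar: reversing the fitted treatment effect in step 5 lowered C to 0.632. In two scenarios with real effects, however, reversal cost only 0.005 (0.789 to 0.784) and 0.016 (0.794 to 0.778), and both versions passed. A reader might infer that C-index cannot tell good allocation from bad. That is too strong.

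Other parts of the reply also stand:
- A reader might infer that the models were tuned on C-index. The tuning score is unnamed, so this cannot be said.
- A reader might infer that any model would pass. Only Cox models were simulated, passing depends on covariate strength, and the document reports that not all ten algorithms were retained.
- PTA is not simply the winner of a contest. It is built from the six retained algorithms, so the 0.7 rule mainly decides membership of the ensemble.
- PTA's AUCs within one treatment (0.839–0.873 for LR, 0.857–0.893 for TACE) are supportive at most. AUC is not C-index, and treatment-by-covariate terms can change ranking within a group.
- Step 4 scores direction of benefit, not the study's rule. Applying the 50% threshold to model A lowers wrong-direction recommendations from 20% to 14% and from 27% to 10%.

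None of this supplies a criterion that assesses the contrast. The results acknowledge significant differences between the LR and TACE groups and state no adjustment beyond entering therapy type as a model factor, so the setting of step 5 cannot be set aside.

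**Conclusion.** The point holds in this form: retention and preference rest on C-index, which can exceed 0.7 with no treatment effect when covariates are strongly prognostic, and no stated criterion assesses the LR-versus-TACE contrast. The selection supports a claim about survival prediction under the treatment received, not the section 4 claim of accuracy when treatments are switched. Ranking by C-index has some sensitivity to a better contrast when confounders are measured, and it can favour a spurious one when they are not (0.760 against 0.732 in step 5).

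These sizes rest on assumed covariate strength, confounding and censoring, and on Cox models. They show what the rule permits and do not estimate PTA's error. A reader might infer that PTA's allocations are wrong; the documents do not show that. They leave the question untested at selection.

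**What to change.** In section 3, keep C-index ≥ 0.7 as a minimum bar for prognosis only. Then, for PTA and each retained model:

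1. Add a held-out (cross-validated) estimate of restricted mean survival under the model's recommendation by the study's own rule of more than 50% in MST, weighted for treatment propensity and treatment-specific censoring. State how patients who meet neither side of that rule are handled.
2. Use a horizon that TACE follow-up supports, for example 36 months (median TACE follow-up 36.1), with 60 months as a sensitivity analysis, since the TACE upper quartile is 54.7.
3. Report differences with bootstrap 95% CIs against treatment as given and against one treatment for all.
4. Add a sensitivity analysis for unmeasured confounding.

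Unless these show a gain, limit the conclusions in section 4, in the results on model selection and in the guideline comparison to survival prediction under the treatment received, and do not call PTA optimal for allocation.

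The cost is analysis code and SAP wording on data already held. The allocation value is noisier than a C-index, still assumes no unmeasured confounding (hence item 4), and may not separate PTA from simpler models.

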To further validate the PTA model, we drew the receiver operating characteristic curves (ROC) and calculated the AUC. The AUC values for 1 year, 3 years, and 5 years were 0.912 (95% confidence interval [CI], 0.887–0.938), 0.914 (95% CI, 0.891–0.937), and 0.928 (95% CI, 0.903–0.953), respectively (Supplement 4A-C and Supplement 5). In addition, the AUCs for TACE treatment were 0.893 (95% CI, 0.858–0.928), 0.857 (95% CI, 0.810–0.904), and 0.858 (95% CI, 0.787–0.929), whereas the AUCs for LR were 0.873 (95% CI, 0.805–0.941), 0.850 (95% CI, 0.797–0.903), and 0.839 (95% CI, 0.779–0.899) at 1, 3, and 5 years, respectively (Supplement 5). The full summary of all indicators (accuracy, sensitivity, specificity, positive predictive value [PPV], negative predictive value [NPV], positive likelihood ratio [PLR], and negative likelihood ratio [NLR]) were compiled in Supplement 5. These results suggested that the PTA model could accurately predict HCC survival at the observed follow-up time.

Additionally, the performance and discriminative ability of clinical guidelines (BCLC, BCLC B sub-classification, HKLC, and ITA.LI.CA stage), tumor-burden-based models (up-to-seven model, four-and-seven model, and six-and-twelve model), and models adopting other parameters (HAP score, mHAP II score, mHAP III score, ALBI score, and MESIAH score) were compared with the PTA model (Table 2). As expected, the 1-, 3- and 5-year auROC and C-index of the PTA model were higher than those of the above mentioned models and prognostic scores. Moreover, three calibration curves were plotted to show the predicted probabilities of death caused by HCC in 1, 3, and 5 years (Supplement 4D-F). The observed survival was within a negligible margin of error of the predicted survival, showing that the performance of the PTA model was overwhelmingly good.

Comparison with clinical guidelines

Next, we compared the discriminative performance of the PTA model in selecting potential candidates with that of the BCLC and HKLC guidelines. As stated above,

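### An integrated Brier score below 0.25 is met by a survival curve with no patient data, and the comparison with 12 systems gives treatment received to PTA only, as far as the text describes

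*Combined protocol and SAP*

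**What the plan says.** On calibration and overall accuracy, section 3 (Model development) defines the Brier score: "The BS represents the mean square difference between observed patient status and predicted survival probabilities; it ranges from 0 to 1". It then sets the threshold: "IBS is defined as an overall estimation of BS; a value lower than 0.25 is deemed applicable in the clinic". The results section on selecting the optimal AI model applies it to all seven retained models, saying that their IBS "was far smaller than 0.25, demonstrating their capability for clinical application". The text gives neither an integration window nor a reference model. The IBS values themselves are in tables and supplements that were not available.

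On the comparison, the section on basic clinical characteristics states that "we perceived therapy type as a pivotal factor in the AI models to simulate a real-world clinical setting". Section 4 (Model estimation) says: "To further estimate the predictive performance of the PTA model, it was compared with other prognostic models". It lists 12 comparators: four staging systems, three tumor-burden rules and five other scores. The metrics are auROC and C-index. The results section on predictive performance reports that "the 1-, 3- and 5-year auROC and C-index of the PTA model were higher than those of the above mentioned models and prognostic scores". It gives AUCs within each treatment group for PTA (for example, "the AUCs for TACE treatment were 0.893" at 1 year), but the text gives none for the comparators.

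**The concern.** There are two issues, and each affects a headline claim.

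**The cut-off.** 0.25 is the Brier score of predicting a probability of 0.5 for everyone. It is also the largest value that a correct covariate-free curve can reach. A rule that such a curve always meets cannot separate a useful model from an uninformative one, so the claim of clinical capability gains no support from it.

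**The comparison.** LR and TACE patients have very different survival. A model that knows which treatment was given can rank LR patients above TACE patients on that fact alone. If the comparators are scored without it, a higher pooled AUC or C-index for PTA may reflect better prognostic information, use of the treatment received, or both. The claim of superiority over 12 systems cannot tell these apart.

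**Working it through.** There is no derivation of 0.25 in the plan to reproduce. The cohort counts do reproduce: 1916 + 3075 = 4991, and 1916/4991 = 38.39%.

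**Inputs** (results, basic clinical characteristics):
- LR share p = 0.3839; TACE share 0.6161.
- LR survival: "The 1-year, 3-year, and 5-year survival probability was 91.7%, 79.6%, and 70.8% for LR allocation".
- TACE survival at the same times: 74.8%, 41.5% and 26.4%.

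**Step 1. Covariate-free Brier score.** Pooled survival is S(t) = p·S_LR(t) + (1−p)·S_TACE(t), and the null Brier score is S(1−S).

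| Year | S | S(1−S) |
|---|---|---|
| 1 | 0.3839×0.917 + 0.6161×0.748 = 0.813 | 0.152 |
| 3 | 0.3839×0.796 + 0.6161×0.415 = 0.561 | 0.246 |
| 5 | 0.3839×0.708 + 0.6161×0.264 = 0.434 | 0.246 |

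S(1−S) peaks at 0.25 when S = 0.5. Since S starts at 1, its time average is always below 0.25.

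**Step 2. Integrated score.** The plan gives survival at three times only, so I assumed a piecewise-exponential curve between them. The treatment-only model gives each group its own curve: p·S_LR(1−S_LR) + (1−p)·S_TACE(1−S_TACE). The swapped model gives each group the other's curve, which adds (S_LR−S_TACE)² to the treatment-only score.

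| Model | IBS, 0–60 months | IBS, 0–36 months |
|---|---|---|
| Null | 0.202 | 0.171 |
| Treatment only | 0.177 | 0.156 |
| LR and TACE curves swapped | 0.284 | 0.218 |

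Linear interpolation moves the first two rows by less than 0.004 and the third by at most 0.009. The validation mix (294/799 LR) gives 0.203 and 0.178 for the first two rows over 0–60 months.

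Scaled Brier is 1 − IBS/IBS(null). At the cut-off over 0–60 months it is 1 − 0.25/0.2019 = −0.24. For treatment alone it is 1 − 0.1766/0.2019 = 0.125. The swapped model, which reverses the contrast the tool is meant to predict, fails the rule over 0–60 months and passes it over 0–36. The verdict on such a model therefore depends on the unstated window.

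**Step 3. Pairs behind a pooled AUC.** Let d be the TACE share of deaths and s the LR share of survivors. Same-treatment pairs make up d(1−s) + (1−d)s, and the rest cross treatments. The AUC of treatment alone is (d+s)/2.

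| Year | d | s | Same treatment | Cross treatment | AUC, treatment alone |
|---|---|---|---|---|---|
| 1 | 0.830 | 0.433 | 0.544 | 0.456 | 0.631 |
| 3 | 0.822 | 0.544 | 0.471 | 0.529 | 0.683 |
| 5 | 0.802 | 0.626 | 0.424 | 0.576 | 0.714 |

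**Step 4. How large could the handicap be?** This is an illustration, not an estimate. I simulated 400,000 patients with normal within-group risk (assumed SD 2 logits) and group intercepts set to match the stated survival. Within-group AUCs came out at 0.863–0.869 for TACE and 0.866–0.888 for LR, close to PTA's reported 0.839–0.893. The treatment-blind score is given the same within-group AUCs.

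| Year | Full-information score | Treatment-blind score | Handicap |
|---|---|---|---|
| 1 | 0.888 | 0.855–0.888 | 0 to 0.03 |
| 3 | 0.892 | 0.814–0.892 | 0 to 0.08 |
| 5 | 0.901 | 0.796–0.901 | 0 to about 0.11 |

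The lower blind value applies if the whole LR–TACE survival gap is due to treatment. The upper value applies if the gap is all case mix that the score can see. With SD from 1.5 to 2.5, the maximum is 0.03–0.04, 0.08 and 0.10–0.11.

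**The case against.** **On the cut-off.** Models are chosen by a C-index of at least 0.7, not by IBS, and a covariate-free curve (C-index 0.5) would be rejected first. The reported IBS values are described as well under 0.25, and AUCs and calibration curves are offered too. PTA's discrimination makes it likely that it beats the null. All this is fair, and it limits the consequence. It does not rescue the rule. The C-index ignores calibration, so a retained model with IBS between about 0.20 and 0.25 over 0–60 months would be worse than no information and still be called applicable. The capability sentence is tied to 0.25 and to nothing else.

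**On the comparison.** Table 2 and the supplements are not visible and may contain a treatment-adjusted step. That PTA was scored with treatment received is inferred: the four input modules in section 4 do not list it. Testing against published systems as published is a legitimate question. LR and TACE patients also differ in tumor size and liver function, which many of the comparators can see in part, so a large share of cross-treatment pairs is not itself evidence of bias. PTA also discriminates within each treatment group, where treatment received cannot help.

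Most of this stands as a limit on size. But the inference is strong: the results call therapy type pivotal in the models, and PTA cannot produce separate LR and TACE predictions without it. The comparators' within-treatment results, which would settle the matter, are absent from the text.

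**Conclusion.** Both parts hold. The 0.25 rule is passed by a curve that uses no patient data (IBS about 0.20 over 0–60 months, 0.17 over 0–36), so passing it does not show clinical applicability. The algebraic bound needs no assumption. The IBS values rest on interpolation and an assumed window, and on training and validation survival being similar. Whether the fitted models beat the null cannot be judged without their IBS values.

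As described, the comparison with the 12 systems is not like for like, with about half of the pairs crossing treatments (46%, 53% and 58%). The handicap to the comparators lies between zero and about 0.03, 0.08 and 0.11 in AUC at 1, 3 and 5 years under the illustrative model, and its true size is unknown. PTA's pooled AUCs of 0.912, 0.914 and 0.928 exceed its within-treatment values, but that gap mixes treatment knowledge with case mix and does not measure inflation. PTA may still win a fair comparison; the present one cannot show by how much. The change should be made, since both the applicability and the superiority claims depend on it.

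**What to change.** 1. State the integration window. Replace the 0.25 cut-off with the validation-set scaled Brier score, 1 − IBS(model)/IBS(null Kaplan-Meier), with a bootstrap confidence interval. Report it also against a treatment-only Kaplan-Meier reference.
2. For each of the 12 systems, fit a Cox model in the training set with the system and treatment received as terms. Compare it with PTA in the validation set. Repeat the comparison within LR and within TACE. Give paired bootstrap confidence intervals for the differences in AUC and C-index.
3. Base the superiority claim on these comparisons. The as-published comparison can stay as a secondary description.

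This needs only existing data and predictions plus 12 simple Cox fits. The margin over the comparators may move either way. Within-LR results will be imprecise: 294 × (1 − 0.917) ≈ 24 deaths by 1 year and 294 × (1 − 0.708) ≈ 86 by 5 years, ignoring censoring. The treatment-added comparison on all 799 validation patients is the more precise of the two. These analyses test prognostic accuracy only; they do not validate the predicted difference between LR and TACE for an individual patient.
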